1.6. Schedule of Activities (SoA) (Part 2)

| Visit Number | | | 01 | 01A | 01B | 01C | 02 | 03 | 04 | 05 | 06 | 07 | 08 | 09 | 10 | 11 | 12 | 13 | 14 | 15 | ED = early discontinuation/withdrawal |
|--------------------------------------------------------|--------------------------|----------|---------------------|-----|-----|-----|------|------|------|-----|-----|------------------|-----|-----|-----------|-----|------|------|------|------|---------------------------------------|
| Time From Start of IV Infusion | | | Pre | EOI | 4hr | 8hr | 24hr | 48hr | 72hr | Wk1 | Wk2 | Wk2 | Wk2 | Wk3 | Wk4 | Wk8 | Wk12 | Wk16 | Wk20 | Wk24 | |
| Day of Study ¹ | | D-1 | D1 | D1 | D1 | D1 | D2 | D3 | D4 | D7 | D8 | D10 ² | D14 | D21 | D28 | D56 | D84 | D112 | D140 | D168 | |
| Clinical Activity | Screen Days -21 to -2 | Check-in | Intervention Period | | | | | | | | | | | | Follow-up | | | | | | |
| Informed consent | X | | | | | | | | | | | | | | | | | | | | |
| Admission to clinic | | X | | | | | | | | | | | | | | | | | | | |
| Discharge from clinic | | | | | | | | | | | X | | | | | | | | | | |
| Inclusion and exclusion criteria | X | X | | | | | | | | | | | | | | | | | | | |
| Demographics | X | | | | | | | | | | | | | | | | | | | | |
| Height, weight, and BMI ³ | X | X | X | | | | | | | | | | | | | | | | | | |
| Vital signs ⁴ | X | X | X | | X | X | X | X | X | X | X | X | X | X | X | X | X | X | X | X | |
| Physical examination ⁵ | X | X | X | X | | X | | | | | | X | | | | | | | | X | |
| Drug Alcohol/Cotinine /history and screen ⁶ | X | X | | | | | | | | | | | | | | | | | | | |

| Visit Number | | | 01 | 01A | 01B | 01C | 02 | 03 | 04 | 05 | 06 | 07 | 08 | 09 | 10 | 11 | 12 | 13 | 14 | 15 | ED = early discontinuation/withdrawal |
|-----------------------------------------------------|--------------------------|----------|---------------------|-----|-----|-----|------|------|------|-----|-----|------------------|-----|-----|-----------|-----|------|------|------|------|---------------------------------------|
| Time From Start of IV Infusion | | | Pre | EOI | 4hr | 8hr | 24hr | 48hr | 72hr | Wk1 | Wk2 | Wk2 | Wk2 | Wk3 | Wk4 | Wk8 | Wk12 | Wk16 | Wk20 | Wk24 | |
| Day of Study ¹ | | D-1 | D1 | D1 | D1 | D1 | D2 | D3 | D4 | D7 | D8 | D10 ² | D14 | D21 | D28 | D56 | D84 | D112 | D140 | D168 | |
| Clinical Activity | Screen Days -21 to -2 | Check-in | Intervention Period | | | | | | | | | | | | Follow-up | | | | | | |

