| Past and Current medical conditions | X | X | | | | | | | | | | | | | | | | | | | |
| Study product administration ⁷ | | | | X | | | | | | | | | | | | | | | | | |
| NRS | | | | X | | | X | | | X | | | | | | | | | | | |
| 12-lead ECG ⁸ | X | | X | X | X | | X | X | X | X | X | X | | | X | | | | X | | |
| Clinical laboratory ⁶ | X | X | | | | | ↔ | | | | | X | X | | X | | X | | X | | X |
| Urinalysis ⁶ | X | X | | | | | | | | | | X | X | | | | | | | | |
| Pregnancy test:(serum) (POCBP only) ⁹ | X | X | | | | | X | | | X | | | X | | X | X | X | X | X | X | |
| FSH ¹⁰ | X | | | | | | | | | | | | | | | | | | | | |
| HIV and hepatitis B and C ⁶ | X | | | | | | | | | | | | | | | | | | | | |

| Visit Number | | | 01 | 01A | 01B | 01C | 02 | 03 | 04 | 05 | 06 | 07 | 08 | 09 | 10 | 11 | 12 | 13 | 14 | 15 | ED = early discontinuation/withdrawal | |
|-------------------------------------|--------------------------|----------|---------------------|-----|-----|-----|------|------|------|-----|-----|------------------|-----------|-----|-----|-----|------|------|------|------|---------------------------------------|--|
| Time From Start of IV Infusion | | | Pre | EOI | 4hr | 8hr | 24hr | 48hr | 72hr | Wk1 | Wk2 | Wk2 | Wk2 | Wk3 | Wk4 | Wk8 | Wk12 | Wk16 | Wk20 | Wk24 | | |
| Day of Study ¹ | | D-1 | D1 | D1 | D1 | D1 | D2 | D3 | D4 | D7 | D8 | D10 ² | D14 | D21 | D28 | D56 | D84 | D112 | D140 | D168 | | |
| Clinical Activity | Screen Days -21 to -2 | Check-in | Intervention Period | | | | | | | | | | Follow-up | | | | | | | | | |
| Test for SARS-CoV-2 ¹¹ | X | X | | | | | | | | | | | | | | | | | | | | |
| Timed PK sample ¹² | | | X | X | X | | X | X | X | X | | | X | X | X | X | X | X | X | X | X | |
| CCI | | | | | | | | | | | | | | | | | | | | | | |
| Recording of AEs/SAEs ¹³ | | | | | | | | | | | | | | | | | | | | | X | |
| Concomitant medication review | | | | | | | | | | | | | | | | | | | | | X | |

AE = adverse event; BMI = body mass index; COVID-19 = coronavirus disease; EOI = end of infusion; FSH = follicle-stimulating hormone; HIV = human immunodeficiency virus; IV = intravenous; NRS = Numeric Rating Scale; PK = pharmacokinetic(s); POCBP = participant of childbearing potential; SAE = serious adverse event; SARS-CoV-2 = severe acute respiratory syndrome-related coronavirus-2

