9.3.3. Secondary Endpoints/Estimands Analysis

9.3.3.1. Pharmacokinetic Analysis

Serum GSK3810109 concentration-time data will be analyzed by PPD, under the oversight of Clinical Pharmacology Modeling & Simulation department within GSK/ViiV, using non-compartmental methods with *Phoenix® WinNonlin®* Version 8.0 or higher. Statistical analysis will be performed by PPD, under the oversight of Biostatistics, GSK/ViiV. Calculations will be based on the actual sampling times recorded during the study. Estimands are presented in Section 3.

Based on the individual concentration-actual time data the following serum PK parameters for GSK3810109 will be estimated as data permit:

AUC(0-inf) – Area under the plasma concentration-time curve from time zero extrapolated to infinity

AUC(0-t) – Area under the plasma concentration-time curve from time zero to time of last observed quantifiable concentration

Cmax – Maximum observed concentration

Tmax – Time of maximum observed concentration

t1/2 – Apparent terminal phase half-life

Summary statistics (arithmetic mean, geometric mean, median, standard deviation, minimum, maximum, and coefficient of variation) will be summarized.

Other PK parameters, e.g. clearance, volume of distribution at steady state, and volume of distribution may also be derived as appropriate.

Blood concentration-time data from different parts of the study may be analyzed using a population approach. A non-linear mixed effects model will be used to determine population PK parameters and identify relevant covariates (e.g., age, weight, or disease related covariates). The data from this study may be combined with the data from other studies for a population PK analysis, which will be reported separately.

Further details of the PK analysis will be provided in the SAP.

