### **4.3. Secondary Endpoint(s) Analyses**

#### **4.3.1. Supportive secondary endpoint(s)**

##### **Definition of Secondary PK Endpoints:**

The following serum PK parameters of GSK3810109 will be determined as data permit:

AUC(0-inf): Area under the serum concentration-time curve from time zero (pre-dose) extrapolated to infinite time; to be calculated using the linear trapezoidal rule for each incremental trapezoid and the log trapezoidal rule for each decremental trapezoid.

AUC(0-t): Area under the serum concentration-time curve from time zero (pre-dose) to the time of the last quantifiable concentration; to be calculated using the linear trapezoidal rule for each incremental trapezoid and the log trapezoidal rule for each decremental trapezoid.

Cmax: Maximum observed serum concentration determined directly from the concentration-time data.

Tmax: Time to reach maximum observed serum concentration

t1/2: Apparent terminal phase half-life (if possible)

Additional PK parameters may be calculated as data permit:

CL/F: Apparent total body clearance following extravascular administration

CL: Total body clearance following intravenous administration

Vz/F: Apparent volume of distribution following extravascular administration

Vss: Volume of distribution at steady state calculated for intravenous administration

*PK Analyses:*

Pharmacokinetic parameters will be calculated by standard non-compartmental analysis according to GSK guideline VQD-GUI-000722 (6.0): Non-Compartmental Analysis of Pharmacokinetic Data and using the currently supported version of Phoenix WinNonlin (8.0 or higher) or using the currently supported version of SAS (9.4 or higher). All calculations of non-compartmental parameters will be based on actual sampling times.

Summary statistics (arithmetic mean, geometric mean, median, 95% CI [arithmetic and geometric], standard deviation [arithmetic and on ln-scale], minimum, maximum, and geometric between-participant CV (%CVb) for serum PK parameters will be summarized.

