### **4.7. Interim Analyses**

An interim analysis is planned after all participants receiving SC administration in Part 1 complete the study. At that stage, all cleaned data available for participants receiving IV administration in Part 2 will also be included and analysed. The interim analysis is planned to enable a preliminary assessment of the safety and PK of this compound before final analysis is performed. The final analysis, on the other hand, will be performed after all database cleaning activities have been completed and final database lock has been declared by the data management.

All safety analyses mentioned in the SAP will be conducted as a part of interim analysis. PK analyses will use nominal sampling times and summary outputs from WinNonlin. As with the final analysis, no formal research hypothesis will be statistically tested in this study.

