## **5. SAMPLE SIZE DETERMINATION**

The number of participants in this study is based on clinical and practical considerations and not on a formal statistical power calculation. The total sample size of approximately 8 participants in each part is considered sufficient for the objectives of the study.

A sufficient number of participants will be enrolled to ensure approximately 8 participants complete each part of the study.

Participants who withdraw prior to study completion may be replaced.

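### SAP 4.3.1 does not exempt Tmax from arithmetic and geometric 95% CIs; on about eight values confined to sample times these are not valid error bars and can start before the infusion has ended

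*SAP*

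**What the plan says.** SAP 4.3.1 lists five serum PK parameters as secondary endpoints, among them "Tmax: Time to reach maximum observed serum concentration". Protocol 9.3.3.1 defines the same endpoint as "Tmax – Time of maximum observed concentration".

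Under PK Analyses, SAP 4.3.1 then sets out one list for serum PK parameters: "Summary statistics (arithmetic mean, geometric mean, median, 95% CI [arithmetic and geometric], standard deviation", followed by minimum, maximum and geometric between-participant CV. No parameter is excepted.

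Three other places give a list without confidence intervals, again covering Tmax: the PK estimand in SAP 1.1, the PK estimand in Protocol Section 3, and Protocol 9.3.3.1. SAP 4.8 declares no changes from the protocol amendment on which the SAP is based.

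For the final analysis, "All calculations of non-compartmental parameters will be based on actual sampling times". For the interim, "PK analyses will use nominal sampling times and summary outputs from WinNonlin". On size, SAP Section 5 says: "The total sample size of approximately 8 participants in each part is considered sufficient for the objectives of the study".

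The Part 2 schedule (Protocol 1.6) has the early columns "Pre | EOI | 4hr | 8hr | 24hr | 48hr | 72hr". The row "Timed PK sample" is marked at all of these except 8 h, and then from Week 1 onward, so the IV sampling grid jumps from 4 h to 24 h.

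**The concern.** Tmax is the clock time of whichever sample happened to be highest. It takes a handful of unevenly spaced values, and in a small group most participants may share one of them. A t-interval, on the hour or the log scale, treats eight such values as draws from a normal or log-normal distribution.

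Two things follow. The interval can extend to times at which no Tmax could have been observed, before the first post-dose sample or even before dosing. And its 95% label need not hold. The mean also responds to the spacing of the schedule: with seven participants at 1 h, moving the eighth from 4 h to 24 h moves the mean from 1.4 h to 3.9 h.

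At stake is the presentation of one of five named secondary PK endpoints, in results that Protocol 9.4 says will help to plan later studies.

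**Working it through.** The documents state no Tmax figure, so there is nothing of the plan's own to reproduce. The check asks what the planned intervals would show.

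**Inputs from the documents**
- n = 8 in Part 2 (SAP Section 5), so 7 degrees of freedom, t(0.975) = 2.365 and t/√8 = 0.836.
- End of infusion (EOI) at about 1 h, at most 2 h (Protocol 6.2).
- Later PK samples at 4 h, 24 h, 48 h, 72 h and beyond (Protocol 1.6). The column header counts from the start of infusion, while the PK footnote counts from its end, so the 4 h draw may be about 5 h after the start.

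**Assumed, because the documents do not give it:** how the eight Tmax values fall over these times. A range is shown.

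**Formula.** Let k of 8 participants peak at a later time a + d and the rest at EOI time a. Then mean = a + kd/8 and SD = d·√(k(8 − k)/56). The arithmetic lower limit is a + d·c, where c = k/8 − 0.836·√(k(8 − k)/56):

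| k | c |
|---|---|
| 1 | −0.171 |
| 2 | −0.137 |
| 3 | −0.058 |
| 4 | +0.053 |

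So with two distinct times the lower limit precedes EOI for k = 1, 2 or 3, whatever the delay, and not for k = 4 or more. On the log scale the lower limit is a·r^c, where r is the ratio of the later time to EOI. The same k apply, but the limit is never negative.

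The arithmetic limit is negative only if d > a/|c|. At a = 1 h that means a delay above 5.9 h (k = 1), 7.3 h (k = 2) or 17.3 h (k = 3).

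**Results, EOI = 1 h**

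| Late peak | k | Arithmetic 95% CI (h) | Geometric 95% CI (h) |
|---|---|---|---|
| none | 0 | 1 to 1 (SD 0) | 1 to 1 |
| 4 h | 1 | 0.49 to 2.26 | 0.79 to 1.79 |
| 4 h | 2 | 0.59 to 2.91 | 0.83 to 2.42 |
| 4 h | 3 | 0.83 to 3.42 | 0.92 to 3.06 |
| 4 h | 4 | 1.16 to 3.84 | 1.08 to 3.72 |
| 24 h | 1 | −2.92 to 10.67 | 0.58 to 3.81 |
| 24 h | 2 | −2.15 to 15.65 | 0.65 to 7.57 |
| 24 h | 3 | −0.33 to 19.58 | 0.83 to 13.03 |
| 24 h | 4 | 2.22 to 22.78 | 1.18 to 20.27 |

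Worked line, seven at 1 h and one at 24 h: mean = 1 + 23/8 = 3.875; SD = 23·√(7/56) = 8.132; half-width = 0.836 × 8.132 = 6.80; limits −2.92 and 10.67.

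Variations: with the 4 h draw at 5 h, the k = 1 arithmetic lower limit is 0.32 h. With EOI at 2 h, one late peak at 4 h gives 1.66 to 2.84 h, and one at 24 h gives −1.75 to 11.25 h.

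Eight participants can split over EOI, 4 h and 24 h in 45 ways. Of these, 20 put the arithmetic lower limit before EOI and 11 make it negative. These are counts of patterns, not probabilities.

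**Coverage.** Exact multinomial sums for n = 8 and EOI = 1 h, under assumed probabilities of peaking at EOI / 4 h / 24 h:

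| Assumed probabilities | Coverage of arithmetic 95% CI | Lower limit before EOI | Lower limit negative |
|---|---|---|---|
| 1 / 0 / 0 | degenerate (1 to 1 h) | 0 | 0 |
| 0.95 / 0.05 / 0 | 34% | 34% | 0 |
| 0.9 / 0.1 / 0 | 57% | 57% | 0 |
| 0.8 / 0.2 / 0 | 83% | 78% | 0 |
| 0.5 / 0.5 / 0 | 93% | 36% | 0 |
| 0.3 / 0.7 / 0 | 93% | 6% | 0 |
| 0.9 / 0.05 / 0.05 | 38% | 57% | 34% |
| 0.8 / 0.1 / 0.1 | 57% | 82% | 55% |
| 0.5 / 0.3 / 0.2 | 83% | 84% | 60% |

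The second row shows the mechanism. All eight peak at EOI with probability 0.95^8 = 0.66. The interval is then 1 to 1 h and misses the true mean, 0.95 × 1 + 0.05 × 4 = 1.15 h.

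**The case against.** The best case for leaving the text alone is that it does no harm. No hypothesis is tested and no stated decision rests on a Tmax interval. The median, minimum and maximum are already in the list, and display details are left to a specification document that is not in hand. All of that stands, and it limits the weight of the point. It does not make the intervals valid, and an unseen specification cannot be assumed to drop what the SAP asks for.

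A reader might infer more than the documents support:

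- **That the IV interval will usually reach impossible times.** This needs a distribution for Tmax, an assay error and an early decline curve, and none is given. Protocol 4.3 gives a 44-day half-life and predicts that levels after 60 mg/kg fall below the average 40 mg/kg Cmax within 72 h. If Cmax is dose-proportional (an assumption), that is a fall to 40/60, or 67%, of peak over three days. It does not fix the difference between EOI and 4 h. Across the assumed cases above, the share runs from 0 to 84%.
- **That negative limits are to be expected.** They need a few peaks at about 24 h or later with the rest mostly at EOI. With peaks only at EOI and 4 h they cannot occur, and the geometric limit is never negative.
- **That covering times between samples is an error.** An interval for a mean need not lie on the sampling grid. Only limits before the first post-dose sample are impossible.

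It is also fair to object that the figures are all for IV dosing. No impossible interval is shown for SC dosing in Part 1. Tmax is confined to sample times there too, so the argument about validity carries over, but the size has not been shown.

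**Conclusion.** The point holds in a limited form. The SAP plans 95% CIs on two scales for a named secondary endpoint that can equal only a sample time. With about eight participants these are not valid error bars: across the eight non-degenerate assumed distributions, coverage of the nominal 95% arithmetic interval ran from 34% to 93%. When one to three participants share a single later peak time and the rest peak at EOI, both intervals start before EOI. The arithmetic one is negative if, with EOI at 1 h, that later time is about 24 h.

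How often such patterns would arise cannot be said from the documents. If all eight peak at EOI, the interval collapses to a point and shows nothing impossible. The examples assume nominal times with EOI at 1 h; actual times in the final analysis would shift them slightly. Because the summary is descriptive and the median and range are already planned, this is a desirable tidy-up and no threat to the study's conclusions.

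**What to change.** In SAP 4.3.1, add that Tmax will be summarised by n, median, minimum and maximum, and that no 95% CIs, geometric statistics or %CVb will be presented for it. Keep the full list for AUC(0-inf), AUC(0-t), Cmax and t1/2. For the two main examples the summary would then read median 1 h, range 1 to 4 h, and median 1 h, range 1 to 24 h.

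The cost is small but not nil. The PK summary lists in SAP 1.1, Protocol Section 3 and Protocol 9.3.3.1 also give means, SD and CV for Tmax. The exception should therefore be recorded in SAP 4.8, which now declares no changes, or those lists should be aligned.

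A smaller change is to drop only the 95% CIs for Tmax. Those three lists contain no CIs, so this conflicts with none of them. It would leave a mean and SD that depend on the sampling schedule.

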#### Individual Item Scores

- Items are rated on a 5-point scale, ranging from 1 **CCI** to 5 **CCI**  

- Higher scores represent worse perception of injection.

Post-injection pain assessment scores based on a NRS from 0 to 10 (0: **CCI**, 10: **CCI**) will be summarized by the study day. NRS assessment scores will be reported by study part. The number and percentage of participants with each pain assessment score will be reported.

For part 1 only, number and percentage of participants reporting ISRs overall and by grade will be provided. The time to onset and duration of the ISRs will be summarized overall and by grade.

All data from PIN and NRS questionnaire assessments will be listed.

#### Laboratory Data:

Laboratory summaries will be presented by study part. Change from baseline in laboratory parameters will be summarized with descriptive statistics by timepoint. All laboratory data related to chemistry, hematology, and urinalysis will be listed separately for participants with any value outside of normal range. A listing will be produced including laboratory data with character results. Summary tables of maximum grade increase post-baseline relative to baseline will also be provided for hematology and clinical chemistry data. A summary table will be provided for worst-case urinalysis data relative to normal range post-baseline relative to baseline.

All liver monitoring/stopping events recorded on the CRF will be listed and summarized. Summary will be presented by study part. The number and percentage of participants with treatment-emergent liver monitoring/stopping events will be reported. Treatment-emergent events are any events that occur after the first dose of the

#### ECG:

ECG data summaries will be reported by study part. Change from baseline will be summarized by timepoint for ECG values. As triplicate measurements of ECG will be taken for all postdose timepoints, average of these assessments will be used for summary tables. For ECG values, the frequency in different categories of maximum post-baseline QTcF values, including maximum change from baseline in QTcF, will be provided. Categories for maximum post-baseline QTcF

values will include no change or decrease to  $\leq 450$  msec, increase to  $>450$  to  $\leq 480$ , increase to  $>480$  to  $\leq 500$  msec, or increase to  $>500$  msec and categories for maximum change from baseline in QTcF will include increase of  $\leq 30$  msec, increase of  $>30$  to  $\leq 60$  msec, or increase of  $>60$  msec. A separate summary table of ECG findings will be created. All ECG values and all ECG findings for participants with an abnormal finding will be listed separately. ECG values will include measurements of heart rate, PR, QRS, QT, and QTcF intervals.

Vital Signs:

Vital signs data summaries will be reported by study part. Vital sign assessments will include temperature, systolic and diastolic blood pressure, respiratory rate, and pulse. Change from baseline over time in vital signs and SPO2 will be summarized with descriptive statistics by timepoint. All vital signs data along with SP02 will be listed.

#### **4.4. Exploratory Endpoint Analyses**

CCI

#### **4.5. Safety Analyses**

As safety endpoints for this study are primary and secondary endpoints, they are included in [Section 4.2](#) and [4.3](#), respectively.

##### **4.5.1. Extent of Exposure**

The administered dose of GSK3810109 and rHuPH20 will be treated as continuous variables and summarized by study part. A listing of study drug exposure data will be produced.

##### **4.5.2. Adverse Events**

An AE is any untoward medical occurrence in a clinical study participant, temporally associated with the use of a study intervention, whether or not considered related to the study intervention.

NOTE: An AE can therefore be any unfavorable and unintended sign (including an abnormal laboratory finding), symptom, or disease (new or exacerbated) temporally associated with the use of a study intervention.

The division of AIDS table for grading the severity of adult and pediatric adverse events (DAIDS, 2017), version 2.1, July 2017 will be used for AE reporting.

Further details on definitions of AEs and SAEs are included in protocol section 10.3. Analyses related to AEs are described in [Section 4.2](#)

#### **4.5.2.1. COVID-19 Assessment and COVID-19 AEs**

All COVID-19 assessments and symptoms will be listed. Separate summaries will be presented for COVID-19 assessments and symptoms. The summaries will be produced by study part. All COVID-19 related analyses will be based on the Safety Analysis Set.

### **4.6. Other Analyses**

Past/ current medical conditions information recorded on the CRF will be presented in a listing and summarized. The summary will be produced by past/current medical conditions as well as the study part. This output will be based on the Safety Analysis Set.

